2.2. Rationale for conducting this study

We hypothesized that there is a homeostatic regulation of body weight. Results from experiments based on this hypothesis demonstrate that increased loading in rodents reversibly decreases the biological body weight via reduced food intake. The same mechanism has also been shown to be functioning in humans suffering from obesity in a short-term proof of concept clinical study [1]. This novel homeostat for body weight regulates body fat mass independently of fat-derived leptin, revealing two independent negative feed-back systems for fat mass regulation. In rodents we have shown that loading improves glucose tolerance. [5] We now want to investigate if a longer clinical study will result in a more pronounced decrease in body weight and fat mass, and also investigate more specifically if there is a decrease in visceral fat mass. We also want to investigate if loading

Study code: ATLAS
Version No: 14.9

Date: 2021-02-01

for a 5 week period has an effect on metabolic parameters and cardiovascular risk factors in humans.

2.3. Risk/Benefit evaluation

In general, this is a study with few risks. The weight vests used in this experiment are daily used by thousands of people for exercise. During previous experiments on 72 subjects for three weeks no serious adverse events were reported. In the high load group, there was a higher reporting of musculoskeletal adverse events (1 person experienced arthralgia, 2 myalgia, 2 pain in lower extremity, 2 swelling of ankle and/or foot). This is contrasted to 1 person experiencing musculoskeletal adverse events in the low load group (1 myalgia). However, only one subject from the high load group and one subject from the low load group discontinued the study due to musculoskeletal adverse events. It is probable that the musculoskeletal adverse events are due to increased axial loading. However, it should be noted that the risks of wearing a weight vest for several weeks in a row are largely unknown. No serious adverse event was reported in any of the treatment groups. [1]

To minimize the risks we have decided to include only healthy obese subjects consuming no or few medications. The trial will include availability of medically trained personnel, such as physicians and experienced nurses. The trial is to be performed at the Sahlgrenska University Hospital. Study subjects are allowed to withdraw their participation from the study at any time.

Blood sampling can be experienced as somewhat uncomfortable by a few individuals. However, it is generally free from complications. In some subjects, there may be small local bruising or inflammation. We may fail to get venous blood from 5-10% of these obese subjects which may cause some additional suffering and increase the risk of complications.

We plan to perform CT-scans and Dual-energy X-ray absorptiometry (DXA) on two separate occasions for measurement of visceral fat, liver fat and body composition at baseline and after 5 weeks. These procedures will entail exposure to a small dose of radiation. Possible unexpected abnormal findings during the CT- or DXA-scans will be investigated and followed up according to the treatment recommendations at the Sahlgrenska University Hospital.

Energy expenditure will be measured with doubly labeled water which is considered completely safe. [12] The isotopes that are used are deuterium (hydrogen-2) and oxygen-18. Both isotopes are stable, meaning that there is no radiation from the molecules and no risk of decay. Both the hydrogen and oxygen isotope are present in lower concentration in normal drinking water.

24-hour ECG registration will be performed on two occasions during the study. This is a safe and non-invasive method. The ECG will be analyzed by an experienced biomedical analysist and if needed looked on by a cardiologist.

Appropriate measures are taken to minimize risk for Covid-19 infection transmission to participants and personnel at Clinical Trial Center at Gothia Forum.

In summary there are no direct benefits to the study subjects. However, we believe the risks to be very low compared to the potential of exploring a new physiological mechanism; a mechanism with potentially important applications such as new obesity treatments which there is a great need for.

Study code: ATLAS
Version No: 14.9

Date: 2021-02-01

3. STUDY OBJECTIVES AND ENDPOINTS

3.1. Primary and secondary objective(s)

Are described in table 2 under section 3.2.

3.2. Primary and secondary endpoint(s)

Are described below in table 2.

Table 2.

Nr.	Primary Objective:	Primary Variables/Measures:
1.	To determine if wearing a weight vest with 11 % of body weight for 8 hours/day for 5 weeks decreases body weight in obese subjects.	Change in body weight (in % of baseline body weight) between day 35 and baseline in the high load group compared with low load group.
	Secondary Objectives:	Secondary Variables/Measures:
2.	To determine if wearing a weight vest with 11 % of body weight for 8 hours/day for 5 weeks decreases absolute body weight in obese subjects.	Change in body weight in absolute values (g) between day 35 and baseline in the high load group compared with low load group.
3.	To determine if wearing a weight vest with 11 % of body weight for 8 hours/day for 15 days decreases body weight in obese subjects.	Change in body weight between day 15 and baseline. Change measured in both absolute values (g) and % of baseline body weight in the high load group compared with low load group.
4.	To determine if wearing a weight vest with 11 % of body weight for 8 hours/day for 4 weeks decreases body weight in obese subjects.	Change in body weight between day 28 and baseline. Change measured in both absolute values (g) and % of baseline body weight in the high load group compared with low load group.
5.	To determine if wearing a weight vest with 11% of body weight for 8 hours/day for 5 weeks affects levels of total abdominal fat in obese subjects.	Change in levels of total abdominal fat between day 35 and baseline. Change measured in both absolute values (cm²) and % of baseline value from CT images of the abdomen. Changes in the high load group compared with low load group.
6.	To determine if wearing a weight vest with 11% of body weight for 8 hours/day for 5 weeks affects levels of subcutaneous fat in obese subjects.	Change in levels of subcutaneous fat between day 35 and baseline. Change measured in both absolute values (cm²) and % of baseline value from CT images of the abdomen. Changes in the high load group compared with low load group.
7.	To determine if wearing a weight vest with 11% of body weight for 8 hours/day for 5 weeks affects levels of visceral fat in obese subjects.	Change in levels of visceral fat between day 35 and baseline. Change measured in both absolute values (cm²) and % of baseline value from CT images of the abdomen. Changes in the high load group compared with low load group.

Study code: ATLAS
Clinical Study Protocol Version No: 14.9

Detail 2021 03

Date: 2021-02-01

8.	To determine if wearing a weight vest with 11% of body weight for 8 hours/day for 5 weeks affects ratio of subcutaneous fat to visceral fat in obese subjects.	Change in levels of subcutaneous fat compared to changes in levels of visceral fat between day 35 and baseline. Change measured in both absolute values (cm²) and % of baseline values from CT images of the abdomen. Ratio in the high load group compared with low load group.
9.	To determine if wearing a weight vest with 11% of body weight for 8 hours/day for 5 weeks affects levels of liver fat in obese subjects.	Change in levels of liver fat between day 35 and baseline. Change measured in both absolute values (Hounsfield Units (HU)) and % of baseline value on CT images of the abdomen. Changes in the high load group compared with low load group.
10.	To determine if wearing a weight vest with 11% of body weight for 8 hours/day for 5 weeks causes changes in topographic CT images.	CT image analysis performed to investigate any differences between day 35 and baseline, for example with respect to change in volume or intensity. Change measured in both absolute and relative values from CT images of the abdomen. Changes in the high load group compared with low load group.
11.	To determine if wearing a weight vest with 11 % of body weight for 8 hours/day for 5 weeks affects fat mass, fat free mass or water mass in obese subjects.	Change in levels of fat mass, fat free mass and water mass between day 35 and baseline. Changes measured in both absolute values (g) and % of baseline value with bioelectrical impedance analysis (BIA) and Dual-energy X-ray absorptiometry (DXA). Water mass only measured using BIA. Changes in the high load group compared with low load group.
12.	To determine if wearing a weight vest with 11 % of body weight for 8 hours/day for 15 days affects fat mass, fat free mass or water mass in obese subjects	Change in levels of fat mass, fat free mass and water mass between day 15 and baseline. Changes measured in both absolute values (g) and % of baseline value with bioelectrical impedance analysis (BIA). Changes in the high load group compared with low load group.
13.	To determine if wearing a weight vest with 11 % of body weight for 8 hours/day for 28 days affects fat mass, fat free mass or water mass in obese subjects	Change in levels of fat mass, fat free mass and water mass between day 28 and baseline. Changes measured in both absolute values (g) and % of baseline value with bioelectrical impedance analysis (BIA). Changes in the high load group compared with low load group.
14.	To determine if wearing a weight vest with 11% of body weight for 8 hours/day for 5 weeks affects waist circumference in obese subjects.	Change in waist circumference between day 35 and baseline. Change measured in both absolute value (cm) and % of baseline value using measuring tape. Change in the high load group compared with low load group.

Study code: ATLAS Clinical Study Protocol Version No: 14.9

Date: 2021-02-01

15.	To determine if wearing a weight vest with 11% of body weight for 8 hours/day for 15 days affects waist circumference in obese subjects.	Change in waist circumference between day 15 and baseline. Change measured in both absolute value (cm) and % of baseline value using measuring tape. Change in the high load group compared with low load group.
16.	To determine if wearing a weight vest with 11% of body weight for 8 hours/day for 28 days affects waist circumference in obese subjects.	Change in waist circumference between day 28 and baseline. Change measured in both absolute value (cm) and % of baseline value using measuring tape. Change in the high load group compared with low load group.
17.	To determine if wearing a weight vest with 11 % of body weight for 8 hours/day for 5 weeks affects serum concentrations of circulating proteins, metabolites or electrolytes.	Change in serum concentration of: glucose, HbA1c, insulin, HDL, LDL, TAG, Free Fatty Acids, Glycerol, FGF21, osteocalcin, FGF23, FGF15, sclerostin, lipocalin2, leptin, ghrelin, GLP-1, GLP-2, CCK, (3-36) PYY, glucagon, renin, testosterone, estrogens, CRP, methoxynorepinephrine, Na, K, Cl, Ca or creatinine between day 35 and baseline. Change measured in both absolute values and % of baseline values. Exploratory analysis in serum of other circulating proteins, metabolites or electrolytes may be performed. Analysis in form of proteomics or metabolomics may also be executed. Change in the high load group compared with low load group.
18.	To determine if wearing a weight vest with 11 % of body weight for 8 hours/day for 15 days affects serum concentrations of circulating proteins, metabolites or electrolytes.	Change in serum concentration of for example: glucose, HbA1c, insulin, HDL, LDL, TAG, Free Fatty Acids, Glycerol, FGF21, osteocalcin, FGF23, FGF15, sclerostin, lipocalin2, leptin, ghrelin, GLP-1, GLP-2, CCK, (3-36) PYY, glucagon, renin, testosterone, estrogens, CRP, methoxynorepinephrine, Na, K, Cl, Ca or creatinine between day 15 and baseline. Change measured in both absolute values and % of baseline values. Exploratory analysis in serum of other circulating proteins, metabolites or electrolytes may be performed. Analysis in form of proteomics or metabolomics may also be executed. Change in the high load group compared with low load group.

Study code: Clinical Study Protocol Version No:

Date: 2021-02-01

ATLAS

14.9

19.	To determine if wearing a weight vest with 11% of body weight for 8 hours/day for 3 weeks affects physical activity in obese subjects.	Change in physical activity between day 21 and baseline. Measured as time distribution in a spectrum of physical activity intensities assessed by accelerometer worn for 24 hours a day for one week. Change measured in both absolute value and % of baseline value. Changes compared between measurements during intervention (day 15 to 21) and baseline (day -13 to -7). Change in the high load group compared with low load group.
20.	To determine if wearing a weight vest with 11% of body weight for 8 hours/day for 4 weeks affects energy expenditure in obese subjects.	Change in energy expenditure between day 28 and baseline. Change measured in both absolute value (Joules per day) and % of baseline value using the doubly labeled water method. Changes compared between measurement during intervention (day 14 to 28) and baseline (day -14 to 0). Change in the high load group compared with low load group.
21.	To determine if wearing a weight vest with 11% of body weight for 8 hours/day for 4 weeks affects food intake in obese subjects.	Change in food intake between day 28 and baseline. Change measured in both absolute value (calories) and % of baseline value using the validated questionnaire Short Dietary Questionnaire (SDQ). Changes compared between measurement during intervention (day 14 to 28) and baseline (day -14 to 0). Change in the high load group compared with low load group.
22.	To determine if wearing a weight vest with 11 % of body weight for 8 hours/day for 2 weeks affects autonomic nervous system activity in obese subjects	Change in heart rate variability (HRV) between day 15 and baseline. Change measured in both absolute values and % of baseline values using 24-hour ECG monitoring. Changes measured at day 15 compared with baseline (day -13). Change in the high load group compared with the low load group.
23.	To determine if waist circumference in obese subjects has changed at follow up visit 2 weeks after the end of intervention.	Change in waist circumference between day 49 and day 35. Change measured in both absolute value (cm) and % of baseline value using measuring tape. Change in the high load group compared with low load group.
24.	To determine if body weight in obese subjects has changed at follow up visit 2 weeks after the end of intervention.	Change in body weight between day 49 and day 35. Change measured in both absolute values (g) and % of baseline body weight in the high load group compared with low load group.

Study code: ATLAS
Clinical Study Protocol Version No: 14.9
Date: 2021-02-01

25.	To determine if fat mass, fat free mass or water mass in obese subjects have changed at follow up visit 2 weeks after the end of intervention.	Change in levels of fat mass, fat free mass and water mass between day 49 and day 35. Changes measured in both absolute values (g) and % of baseline value with bioelectrical impedance analysis (BIA). Changes in the high load group compared with low load group.
26.	To determine if there is any change at follow up visit 2 weeks after the end of intervention in serum concentrations of circulating proteins, metabolites or electrolytes.	Change in serum concentration of: glucose, HbA1c, insulin, HDL, LDL, TAG, Free Fatty Acids, Glycerol, FGF21, osteocalcin, FGF23, FGF15, sclerostin, lipocalin2, leptin, ghrelin, GLP-1, GLP-2, CCK, (3-36) PYY, glucagon, renin, testosterone, estrogens, CRP, methoxynorepinephrine, Na, K, Cl, Ca or creatinine between day 49 and day 35. Change measured in both absolute values and % of baseline values. Exploratory analysis in serum of other circulating proteins, metabolites or electrolytes may be performed. Analysis in form of proteomics or metabolomics may also be executed. Change in the high load group compared with low load group.

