6.	To determine if wearing a weight vest with 11% of body weight for 8 hours/day for 5 weeks affects levels of subcutaneous fat in obese subjects.	Change in levels of subcutaneous fat between day 35 and baseline. Change measured in both absolute values (cm²) and % of baseline value from CT images of the abdomen. Changes in the high load group compared with low load group.			
7.	To determine if wearing a weight vest with 11% of body weight for 8 hours/day for 5 weeks affects levels of visceral fat in obese subjects.	Change in levels of visceral fat between day 35 and baseline. Change measured in both absolute values (cm²) and % of baseline value from CT images of the abdomen. Changes in the high load group compared with low load group.			
8.	To determine if wearing a weight vest with 11% of body weight for 8 hours/day for 5 weeks affects ratio of subcutaneous fat to visceral fat in obese subjects.	Change in levels of subcutaneous fat compared to changes in levels of visceral fat between day 35 and baseline. Change measured in both absolute values (cm²) and % of baseline values from CT images of the abdomen. Ratio in the high load group compared with low load group.			

Study code: ATLAS Clinical Study Protocol Version No: 14.9

Date: 2021-02-01

9.	To determine if wearing a weight vest with 11% of body weight for 8 hours/day for 5 weeks affects levels of liver fat in obese subjects.	Change in levels of liver fat between day 35 and baseline. Change measured in both absolute values (Hounsfield Units (HU)) and % of baseline value on CT images of the abdomen. Changes in the high load group compared with low load group.
10.	To determine if wearing a weight vest with 11% of body weight for 8 hours/day for 5 weeks causes changes in topographic CT images.	CT image analysis performed to investigate any differences between day 35 and baseline, for example with respect to change in volume or intensity. Change measured in both absolute and relative values from CT images of the abdomen. Changes in the high load group compared with low load group.

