7.1.2.3. Computed Tomography (CT) scan

A CT scan of the abdomen and the liver will be performed at day 0 (+/- 3 days) and day 35 (+/- 3 days). The CT scans will be performed at the department of radiology at the Sahlgrenska University Hospital, using a computer tomograph of the model Siemens Somatom Force. Research nurses [name] and [name] have contributed to the development of the protocol and are responsible for the execution of these examinations.

Each CT scan will provide images, from each image the area (cm²) of visceral fat, subcutaneous fat and total abdominal fat (subcutaneous plus visceral fat) will be measured. An average of the areas from these images will be calculated for each fat depot. Change in average area of visceral fat, subcutaneous fat and total abdominal fat will then be analyzed. Liver fat will be measured in Hounsfield units (HU) on CT images. CT image analysis from topographic images may also be performed to investigate any differences between day 35 and baseline, for example with respect to change in volume or intensity. Changes will be analyzed in both absolute values and relative values (% of baseline value) from CT images of the abdomen.

The images will be stored in the radiology department imaging storage database named *Bild och Funktionsregistret* (BFR) at Sahlgrenska University Hospital. After the CT scans an experienced radiologist at Sahlgrenska University Hospital will examine all scans for accidental medical findings. The investigator will be informed of any accidental medical findings of relevance as judged by the radiologist. The investigator is then responsible to determine and handle further need of investigation of the finding.

Study code: ATLAS
Version No: 14.9

Date: 2021-02-01

Images from both CT scans will then be pseudonymized and transferred to the Uppsala University to be analyzed by researchers with expertise in automated image analysis. Images will be sent on a portable secure hard drive. Associate [name], Uppsala University, is responsible for the interpretation of these measurements.

7.1.2.4. 24-hour ECG recording

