The accelerometers are to be initialized, and raw data to be downloaded by study staff at Center for Health and Performance at University of Gothenburg using the manufacturer's software (OMGUI Configuration and Analysis Tool, Axivity Ltd, UK). These measurements will be used to calculate possible differences in physical activity. Outcome measurements will be time distribution in a spectrum of physical activity intensities [15]. Change in time distribution will then be compared in absolute and in relative values (in % of baseline physical activity) between measurements during intervention (day 15 to 21) and baseline (day -13 to -7). Change in the high load group will be compared with the low load group. Unauthorized personnel will not have access to the data from the accelerometers. [name] [name], University of Gothenburg and Sahlgrenska University Hospital, is responsible for the interpretation of these measurements.

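### Two exploratory CT endpoints are badly defined: no. 8 uses a ratio of changes where its objective names a ratio of fat levels, and no. 9 takes a percentage of baseline Hounsfield units

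*Protocol*

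**What the plan says.** Both endpoints appear in the protocol's Synopsis (Table 1) and again in the endpoint table of section 3.2.

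**No. 8, fat distribution.** The objective asks whether the heavy vest "affects ratio of subcutaneous fat to visceral fat in obese subjects". The variable is "Change in levels of subcutaneous fat compared to changes in levels of visceral fat between day 35 and baseline", in cm² and as a percentage of baseline. The row closes with "Ratio in the high load group compared with low load group".

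**No. 9, liver fat.** The variable is "Change in levels of liver fat between day 35 and baseline", with this scale: "Change measured in both absolute values (Hounsfield Units (HU)) and % of baseline value on CT images of the abdomen". Section 7.1.2.3 confirms the unit, "Liver fat will be measured in Hounsfield units (HU) on CT images", and repeats the relative version for the CT measures as a group: "Changes will be analyzed in both absolute values and relative values (% of baseline value) from CT images of the abdomen".

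Section 9.2.1 classes every secondary endpoint as exploratory. It applies the primary method to them: ANCOVA, with transformation and then a non-parametric analysis if normality fails. The listed covariates are age, BMI, sex, wearing time and share of wearing time spent standing. The baseline value of a CT measure is not among them.

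**The concern.** In no. 8 the objective and the variable are different quantities. A ratio of subcutaneous to visceral fat describes how fat is distributed, and its change shows whether the distribution has shifted. A ratio of two changes does not. It loses the direction of change, and its denominator can lie close to zero in a five-week study, most obviously in the 1% vest arm, where little change is expected.

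In no. 9 a percentage is taken on a scale whose zero is a calibration point. A percentage of baseline is a proportion of something only when zero means none of it. That holds for an area in cm² and for body weight, but not for HU.

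Visceral fat and liver fat are among the measures the Synopsis says the study will monitor, and section 2.2 names visceral fat in the rationale. At stake is a published fat-distribution result that does not answer its question, and a liver-fat percentage whose size depends on where each participant started on the HU scale. Both scales are written into the endpoint definitions, so this is not detail left for a statistical analysis plan.

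**Working it through.** The protocol gives no effect size, SD or baseline distribution for nos. 8 or 9, so there is no stated figure to reproduce. The one input taken from it is the arm size of 25 (section 9.3). All other values below are assumptions.

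**No. 8: loss and gain are not told apart.** Assume baseline areas of 350 cm² subcutaneous (S) and 150 cm² visceral (V), so S/V = 350/150 = 2.333.

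| Quantity | Both shrink (S -20, V -10 cm²) | Both grow (S +20, V +10 cm²) |
|---|---|---|
| Ratio of absolute changes | -20/-10 = 2 | 20/10 = 2 |
| Ratio of percent changes | -5.71%/-6.67% = 0.857 | 5.71%/6.67% = 0.857 |
| S/V at day 35 | 330/140 = 2.357 | 370/160 = 2.3125 |
| Change in log(S/V) | ln(2.357/2.333) = +0.010 | ln(2.3125/2.333) = -0.009 |

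The literal variable is identical in the two columns, on the absolute and on the percent scale. The change in the ratio of levels separates them and has opposite signs.

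**No. 8: stability of the arm mean.** For each participant, the subcutaneous and visceral changes were drawn from a bivariate normal distribution with equal SDs, equal means in SD units and correlation 0.5. The ratio of the two changes was averaged over 25 participants, and this was repeated 4,000 times.

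| Mean visceral change (SD) | Central 95% of arm means | Participants whose visceral change is positive |
|---|---|---|
| 0 | -10.2 to 11.6 | 50% |
| -0.5 | -9.5 to 10.8 | 31% |
| -1 | -8.6 to 7.1 | 16% |
| -2 | -0.9 to 3.2 | 2% |

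The instability falls as the mean visceral change moves away from zero, but it is still severe at -1 SD.

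For contrast, the change in S/V was simulated with areas centred on 350 and 150 cm² (SDs 60 and 40) and each depot changing by -2% on average with an SD of 5%. The central 95% of 25-subject arm means was -0.07 to +0.09, around a baseline ratio near 2.3.

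**No. 9: percent of baseline HU.** Percent change = 100 × change/baseline. For the same change of +5 HU:

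- from 60 HU: 5/60 = +8.3%
- from 10 HU: 5/10 = +50%
- from 0 HU: undefined
- from -5 HU: 5/(-5) = -100%

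The absolute change is +5 HU in every case.

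**The case against.** **Exploratory status.** All secondary endpoints are exploratory, and neither the depot ratio nor liver fat is in the selection listed in section 9.2.1. This stands and sets the severity.

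**Absolute versions are planned.** For no. 9 this stands: absolute HU change is already specified, so the percentage is a redundant companion. For no. 8 it does not help, because the absolute version still sets one change against another. Nos. 6 and 7 do report each depot separately in cm², so the underlying data are not lost.

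**Fallback analysis.** Ranks limit the pull of extreme values, so the wide arm means above need not reach the final test. Ranks cannot supply an undefined value, undo a sign reversal, or turn a ratio of changes into a ratio of levels.

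**No. 8 can be read otherwise.** It could mean a side-by-side comparison or a difference. A difference of percent changes would even approximate the log ratio: in the example above, -5.71% minus -6.67% is +0.95%, against +1.0% on the log scale. But the row ends by comparing a ratio between arms, and nothing in it points to that reading. What is certain is that objective and variable disagree; the ratio of changes is the literal reading, not the only one.

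**Stronger readings the protocol does not support.** A reader might infer that liver fat will be reported with the wrong sign, because higher HU means less fat. No. 9 asks only whether the vest affects liver fat and states no direction, so nothing there is wrong. A reader might also extend the point to physical activity (no. 19), where section 7.1.2.8 says: "Change in time distribution will then be compared in absolute and in relative values (in % of baseline physical activity". A percentage fails there only if a participant has zero baseline time in an intensity band. The protocol defines no bands, does not fix the denominator per band and gives no figure for zero time. Those details may properly be left to an analysis plan.

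**Conclusion.** The point holds for two endpoints, at low severity. In no. 8 the objective and the variable are different quantities. Followed literally, the variable cannot tell joint loss from joint gain, and this needs no assumption. Its instability does rest on assumptions: it is severe when the mean visceral change is within about 1 SD of zero and much smaller at -2 SD, under normal changes with correlation 0.5.

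In no. 9 the dependence on an arbitrary zero holds at every baseline. The dramatic values arise only near or below 0 HU. At clearly positive baselines the percentage can be computed but adds nothing to the absolute change. How many participants will have low baselines cannot be known from the protocol.

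It would go too far to say that group means are bound to be driven by one or two participants, since that assumes near-zero denominators and ignores the fallback. The primary endpoint, a percentage of baseline body weight, has a true zero and is unaffected, as is the sample size.

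**What to change.** **No. 8.** In Table 1 of the Synopsis and the endpoint table of section 3.2, define the variable as the change from baseline to day 35 in the ratio of subcutaneous to visceral area, preferably as the change in log(subcutaneous area/visceral area), compared between arms. The log form treats the two depots symmetrically and never divides by a change. The untransformed change in the ratio would also match the objective.

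**No. 9.** In the same two tables, delete the percent-of-baseline version for liver HU and keep the absolute HU change. In section 7.1.2.3, exempt liver HU from the general sentence on relative values; percent change can stay for the areas in cm². Add baseline HU to the covariates for this endpoint. A note that higher HU means less fat would help readers but corrects no error.

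The cost is a wording change in three places and one extra covariate. The same scans and measurements are used, with no effect on visits, sample size or the primary analysis. It should be made before outcome data are analysed by arm.
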